2.2 Study Rationale

In combination, the above data highlight the need for focused treatment development, especially in veterans who served in the recent conflicts, including Operation Iraqi Freedom (OIF), Operation Enduring Freedom (OEF), and Operation New Dawn (OND). Two promising approaches are Acceptance and Commitment Therapy (ACT) for chronic pain and Mindfulness-Based Relapse Prevention (MBRP). ACT for chronic pain decreases problematic pain avoidance behaviors and enhances engagement in effective and meaningful activities which contribute to fewer pain-related restrictions in functioning over the longer term⁵¹. Mindfulness-Based Relapse Prevention (MBRP) for substance use disorders may be an ideal behavioral intervention for helping individuals cope with the desire, or “craving,” to use opioids, as well as the automatic tendency to use opioids when experiencing pain. MBRP for substance use disorders was designed to target these behaviors, with the ultimate goal of reducing problematic substance use^{52,53}.

While there have been no direct examinations of ACT and MBRP in combination, research in ACT and MBRP separately presents a number of parallel, compatible findings which support their efficacy. We therefore hypothesize that their combination in veterans experiencing chronic pain and opioid-related difficulties will be both appropriate and feasible. Further, we hypothesize that the combination of these treatments will affect specific therapy targets (e.g., pain acceptance and opioid craving) in a manner consistent with existing trials.

[figure not shown]
ACT and MBRP are each promising interventions with good efficacy data^{7,54} and are likely to complement one another in treating this population. Thus, the proposed research is significant in that we are proposing to empirically test a combination of interventions that could greatly decrease pain interference, improve functioning, and decrease opioid misuse among the very large number of veterans treated for chronic pain.

3. STUDY DESIGN

As noted above, the primary objective of the study is to determine the feasibility and acceptability of a combined treatment for veterans with comorbid chronic pain and opioid misuse or dependence, as well as assess mechanisms of change during the combined intervention. Participants will include veterans with chronic pain and opiate misuse, abuse, or dependence who are receiving long-term opioid therapy (i.e., 90+ days) and who are receiving treatment from the Raymond G. Murphy Veterans Affairs (VA) Medical Center in Albuquerque, NM. Treatment will begin in Year 1 and conclude in Year 2 with follow-

up assessment lasting through the first quarter of Year 3. At the time of enrolling in the trial, individuals will participate in a baseline assessment including self-report and behavioral measures. Participants ($n = 120$) will then be randomized to one of two treatment conditions: (1) treatment services-as-usual (i.e., standard care) or (2) standard care with eight weeks of group ACT plus four weeks of group MBRP. Participants will complete assessments at baseline (entry into the study), weekly during the first three months of the study (during treatment), three months after entry in the study (end of treatment), and nine months after entry in the study (six months after treatment conclusion). The trial design is shown in Figure 1.

Figure 1. Proposed Trial Design

Based on the preliminary data described above and our experience in working with chronic pain patients who misuse/abuse their prescription opioids, we hypothesize that the combination of ACT with MBRP may be particularly suited for treating this population. Other interventions (e.g., cognitive-behavioral therapy, exercise therapy) were also considered; however, our recent work has suggested that both ACT and MBRP may be superior or more suitable in comparison to these other interventions. Also, ACT and MBRP are theoretically aligned, which makes their combination more seamless than other interventions that are not theoretically aligned. Several research designs incorporating ACT and MBRP were also considered (e.g., including an MBRP-only condition, a wait-list control group, or a no-treatment control group); however, these designs were ruled out because 1) MBRP was designed and has been empirically supported as an after-care intervention and has not been empirically studied as a stand-alone intervention for chronic pain, and 2) wait-list and no-treatment control groups were considered unethical for a treatment seeking population already enrolled in treatment. We hypothesize that training in ACT will help reduce pain interference and improve functioning and that the addition of the MBRP mindfulness skills to ACT will help individuals with chronic pain who currently meet criteria or are at high risk for opioid misuse to reduce patterns of opioid misuse until they are no longer of clinical concern.

4. SELECTION AND ENROLLMENT OF PARTICIPANTS

Recruitment Sites and Participants— This study will recruit veterans with chronic pain ($n = 120$) who are misusing, abusing, or dependent on prescription opioids. Participants will be recruited from the Co-Occurring Disorders Clinic (a specialty clinic for patients with chronic pain and evidence of problematic opioid use), as well as the Ambulatory Care and Primary Care Clinics of the Raymond G. Murphy VA Medical Center in Albuquerque, New Mexico.

The Albuquerque VA is an ideal recruitment site for the present study for several reasons. First, it has approximately 321,140 veterans enrolled in Primary and Ambulatory Care and facility records indicate that nearly a quarter of these are currently prescribed chronic opioid therapy as defined by a prescription of 90 or more days. Second, the issue of comorbid chronic pain and problematic opioid use has been identified as a priority within this VA, such that a specialty medication management clinic has been established. This clinic receives approximately 25 referrals per month, with only approximately 30% of these appropriate for the primary treatment option of Buprenorphine (an opioid agonist)⁵⁰. These data suggest that there is a large proportion of patients who are seeking help for chronic pain with potential opioid misuse who are in need of intervention beyond the currently available treatment options. These individuals, as well as veterans in Primary and Ambulatory Care, may be appropriate for recruitment into the present study. Finally, the close proximity and history of collaboration between the University of New

Mexico (UNM) and the Albuquerque VA should aid in decreasing institutional barriers and facilitating progress. Historically, Veterans treated at the Albuquerque VA are primarily male, average 62 years of age, and are of considerable racial/ethnic diversity, including over 40% Hispanic and about 10% Native Americans.

Recruitment methods: The study PI and the research team will work closely with staff in Co-Occurring Disorders, Primary and Ambulatory Care clinics at the VA Medical Center. In-service seminars will be held to explain the purpose of the study and eligibility criteria to hospital staff at the beginning of the study and periodically throughout the recruiting period. An IRB approved recruitment flyer will also be distributed to these clinics (see Microsoft Publisher attachments to protocol materials for IRB approved flyer and informational brochure).

Before a patient is contacted by the study team, the patient's primary clinician will be asked to: a) confirm patient is between the ages of 21-65; b) confirm a chronic pain diagnosis of six months or longer; c) review medications to confirm that patient has been prescribed opioids for ninety days or longer; d) confirm that patients pain severity level has been four or greater over the past seven days on a 0 to 10 scale, where 0 is no pain and 10 is worst pain possible and e) provide the patient with the study flier describing the study and invite the patient to meet with the research team to learn about the study and be screened for eligibility. If the patient expresses interest in the study and requests that the study team contact him/her for screening, the primary clinician will then alert the study PI via the electronic medical record or with PKI encrypted email containing name and last four indicating that the patient is interested in being contacted for screening. No assessments will be administered for research purposes, including screening, until the patient has signed the informed consent.

Once potential participants have made voluntary contact with the investigators (e.g. after seeing a study flier at the VA facility) or once a member of the research team makes contact with potential participants after they express interest to their treatment providers, a full screening will take place via telephone to confirm eligibility for the study (using the Telephone Screening Form, which contains all exclusion and inclusion criteria listed in section 5). In order to inquire about PHI relevant to all inclusion and exclusion (i.e., designated special population membership) criteria, the investigators have obtained a HIPPA waiver from the governing IRB. Further, details of the study will also be discussed to better inform potential participants about the study requirements. Potential participants will be free to ask any questions about the study. At no time during the telephone screen is identifiable information collected that can link answers to the potential participant. If participants meet the above eligibility criteria and remain interested in taking part in the study, an appointment will be set up to meet with the participant at the data collection site, which take place in a private office. At this appointment, the participant will complete all baseline assessment information. In the event that a potential participant is ineligible or declines to take part in the study, any protected health information will be destroyed pursuant to VA information security policy. The electronic medical record will be utilized to alert the primary care provider that a patient on his/her panel has been enrolled in the study and which study arm the patient was assigned to. The payment schedule as according to the section of the Protocol on Participant Compensation will be clearly explained to potential participants during the consent process and following assignment into study condition.

4.1 Inclusion Criteria

All participants must meet the following inclusion criteria: 1) be between 21 and 65 years old; 2) have had chronic pain for >6 months in duration; 3) averaged 4 or greater on usual pain intensity over the past week on a scale of 0-10 with medication; 4) daily use of prescribed opioids for chronic pain for at least 90 consecutive days preceding assessment; 5) identified as having current opioid misuse [Current Opioid Misuse Measure (COMM) score of > 12]³ or meeting diagnostic criteria for opiate abuse or dependence based on the Structured Clinical Interview for the DSM (SCID)⁵⁶; 6) consent to randomization of

treatment to usual care with or without ACT+MBRP; 7) be willing to consent to assessment procedures and to be contacted for follow-ups; and 8) the ability to read written English.

4.2 Exclusion Criteria

With regard to exclusionary criteria, participants will not be eligible for study participation if they: (1) meet diagnostic criteria for current substance abuse/dependence on a drug other than opioids, (2) meet diagnostic criteria for a current or past DSM diagnosis of schizophrenia, delusional disorder, psychotic or dissociative disorders, (3) are currently prescribed medications for opioid addiction (e.g., Buprenorphine/Naloxone/Suboxone),, or (4) history of suicide attempts or inpatient hospitalization for risk of suicide in the past six month. In addition, we will screen for significant suicidal ideation (e.g., marked intent or established plan) using a self-report measure at the baseline, post-treatment, and follow-up assessments. If significant ideation exists, the study RA will contact the VA's Acute Psychiatric Clinic, which provides on-call and immediate consultation and liaison services for the VA. The service is often consulted when significant ideation is identified.

During the study period, participants may become ineligible and may be involuntarily removed. The conditions for removal are detailed in the Consent Form. These conditions are summarized as follows: (1) Individuals may be removed if the study team discerns a significant worsening of stress or mood symptoms as a result of study participation, (2) if an participant is incarcerated, they cannot attend treatment sessions and will be removed, (3) if an individual becomes pregnant, their primary care provider will wean them off of opioids (due to documented birth defect risk associated with opioid use) which will render the participant ineligible for the study as they will no longer be taking opioids, and (4) if the participant displays behaviors that are deemed overly disruptive to other participants in the treatment group.

4.3 Study Enrollment Procedures

A brief screening questionnaire that inquires about eligibility criteria will be administered via telephone to patients receiving opioid therapy as part of their treatment for chronic pain at the VA who are interested in participating in the research study. Interested individuals who meet initial screening criteria will be seen at the VA for an in-person screening where the procedures and voluntary nature of the study will be fully explained. Participants will meet with a trained Research Assistant (RA) in a private assessment office at the VA for the opioid use and psychiatric screening and to obtain Human Research Protections Office (HRPO) approved informed consent. The in-person screening will consist of self-reported opioid misuse behaviors on the COMM, as well as a structured clinical interview using the Substance Use Disorders model of the SCID, which will enquire about opioid use patterns.

Anticipated wait time from screening to baseline assessment and randomization. After the initial screening, eligible participants will be scheduled for an in person assessment to complete informed consent and baseline assessments. This assessment will occur within 14 days (and ideally within 7 days) of screening. Immediately following completion of informed consent and assessment, participants will be randomized to treatment condition.

Anticipated wait time from randomization to intervention beginning. We plan to begin at least one new group per month, therefore, wait time for most participants is anticipated to be less than one month from the time of study enrollment. As noted, we have planned for recruitment of eight individuals per month, which corresponds to our target group size. Should recruitment be faster than expected, we can accommodate up to ten individuals in each group to keep waiting times to a minimum. Furthermore, by the third month of providing intervention, we will be running three treatment groups at any one point in time (as each group will receive treatment for three months total). If the participant backlog surpasses six individuals (which is sufficient to compose a group for treatment), we will be able to add a fourth treatment group.

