Interventions and Duration: Intervention Conditions—All participants will continue to receive standard care for chronic pain within the VA. In addition, one-half of participants will be randomized to also receive ACT plus MBRP. **Standard Care:** Participants in all conditions will receive standard treatment as usual at the VA, as indicated by the individual's treatment plan which will not be manipulated by the research team. Consistent with national and VA standards^{14,15}, care at the recruitment sites typically consists of noninvasive interventions, such as analgesic pain medications (e.g., opioids, NSAIDs, anti-epileptics), topical solutions (e.g., lidocaine), physical therapy, and massage, as well as limited invasive interventions (e.g., injections, radiofrequency denervation). **Acceptance and Commitment Therapy (Weeks 2–9):** The ACT intervention is based on the standardized and manualized protocol of [name] and Sorrell¹⁶, which consists of weekly 90-minute group meetings over eight weeks. The protocol has been successfully used in previous clinical trials (e.g., ^{17,18}) and is currently available on the VA's Evidence-Based Practice SharePoint website. Over the course of the group meetings, participants will identify areas of meaningful functioning that have been adversely impacted by pain, learn methods to enhance pain willingness in the service of these meaningful areas, and practice present-focused awareness skills. Group sessions will include discussions of the impact of pain and distress avoidance, identifying alternatives to this avoidance and establish plans for behavior change, demonstration and role-playing exercises, and homework assignments. Participants will be provided with a treatment manual to help guide and inform practice outside of group sessions. Table 1 provides an outline of session content for the eight week ACT intervention. We anticipate enrolling approximately eight patients per group. **Mindfulness Based Relapse Prevention (Weeks 10–13):** The MBRP program is a standardized group psycho-educational intervention that consists of weekly 90-minute group meetings spanning four¹⁹ to eight weeks²⁰. For the current study, we will use the four-week program, which will eliminate redundancy with the ACT protocol (the eight-week MBRP group has some redundancy with ACT) and will also expand upon the 8 weeks of ACT by focusing on reactivity to substance cues, opioid misuse, and nonjudgmental awareness. Briefly, participants will be instructed in mindfulness techniques aimed at increasing concentration, improving awareness, and cultivating a nonjudgmental and accepting attitude toward craving and automatic thought patterns. Group sessions include discussions of mindfulness as a means of coping with craving and painful cognitions, role-playing exercises, meditation practice, and homework assignments. Each participant will be given audio CDs developed specifically for MBRP for independent practice outside of the group sessions.

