1. STUDY OBJECTIVES

1.1 **Primary Study Aims:** Determine the feasibility of an integrated psychosocial treatment (ACT + MBRP) in veterans with chronic pain with evidence of opioid-related problems. Chronic pain patients ($n = 120$) who are receiving opioid therapy and who are identified as opioid misusing, abusing, or dependent will be recruited from the Albuquerque Veterans Administration (VA) Hospital. Participants will be randomized to receive standard care or standard care in addition to ACT+MBRP. **Hypothesis 1: Feasibility of recruitment:** Given the high prevalence of both chronic pain and opioid-related problems in VA populations, we hypothesize it will be possible to recruit our target sample size ($n = 120$) within a 15-18 month timeframe. **Hypothesis 2: Feasibility of retention:** Drop-out rates will be consistent with other trials of similar psychosocial interventions for chronic pain (i.e., < 20%^{5,21-23}).

1.2 **Secondary Study Aims:** To examine weekly progress on specific therapy targets (e.g., pain acceptance, self-compassion, opioid craving) in the interventions in order to identify potential mechanisms of change and to identify the choice of intermediate endpoints for a larger randomized clinical trial.

Hypothesis 1: Evidence of treatment mechanisms: The combined ACT+MBRP treatments will be associated with changes in treatment mechanisms specified within the therapeutic models and in a manner consistent with that of previous work on ACT and MBRP, in comparison with standard care.

Hypothesis 2: Selection of intermediate endpoints: Weekly progress measures will provide data indicating measures of treatment-specific mechanisms that are most sensitive to change. We hypothesize that acceptance of pain discomfort will be most sensitive to change in ACT and that reductions in reactivity to substance craving will be most sensitive to change in MBRP.

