5. STUDY INTERVENTIONS

5.1 Interventions, Administration, and Duration

Intervention Conditions—All participants will continue to receive standard care for chronic pain within the VA. In addition, one-half of participants will be randomized to also receive ACT plus MBRP.

Standard Care: All conditions will also receive standard treatment as usual, as indicated by treatment plan and not manipulated by the research team. Consistent with national and VA standards^{14,15}, care at the recruitment sites typically consists of noninvasive interventions, such as analgesic pain medications (e.g., opioids, NSAIDs, anti-epileptics), topical solutions (e.g., lidocaine), physical therapy, and massage, as well as limited invasive interventions (e.g., injections, radiofrequency denervation).

Acceptance and Commitment Therapy (Weeks 2–9): The ACT intervention is based on the standardized and manualized protocol of [name] and Sorrell¹⁶, which consists of weekly 90-minute group meetings over eight weeks. The protocol has been successfully used in previous clinical trials (e.g.,^{17,18}) and is currently available on the VA's Evidence-Based Practice Sharepoint website. Over the course of the group meetings, participants will identify areas of meaningful functioning that have been adversely impacted by pain, learn methods to enhance pain willingness in the service of these meaningful areas, and practice present-focused awareness skills. Group sessions will include discussions of the impact of pain and distress avoidance, identify alternative to this avoidance and establish plans for behavior change, demonstration and role-playing exercises, and homework assignments. Participants will be provided with a treatment manual to help guide and inform practice outside of group sessions. Table 1 provides an outline of session content for the eight week ACT intervention. We anticipate enrolling approximately eight patients per group.

Table 1: Overview of ACT Treatment Sessions

Session	Objectives and Content
1	
a. Treatment orientation and overview.b. Review treatment history and evaluate it in terms of how it has worked relative to patient's goals and expectations.

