5.2 Handling of Study Interventions

Interventions will be delivered in a group format. The target number of participants for each group will be up to eight individuals, although it is possible to conduct the group with as few as four participants or as many as ten. Both interventions will be manualized as described in section 5.1 above. Due to the nature of the intervention, blinding to condition will not be possible.

Number of therapists: There will be a minimum of two study therapists for each group (one the RA paid on the grant and the other a volunteer RA). Study therapists will be appointed through the University of New Mexico's (UNM) graduate program in clinical psychology. The volunteer RA will receive practicum credit through UNM in lieu of payment. All therapists will be advanced post-Masters degree doctoral students (i.e. with necessary approval of the UNM's Clinical Committee to engage in clinical work) who will have received four and one half days of training (32.5 hours total) in ACT (provided by [name]; training completed January 2015) and MBRP (provided by [name]; training completed December 2014). Prior to leading any treatment sessions, therapists will be required to demonstrate a minimum level of competency, as outline by ACT and MBRP training guidelines. Instructors will also receive weekly supervision from an outside supervisor with specific expertise in ACT and MBRP.

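### Eight recruits a month is the rate for both arms, so ACT+MBRP groups gain about four a month; separately, the assessment-timing sections conflict once the stated wait for a group is applied

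*Combined protocol and SAP*

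**What the plan says.** **Inflow.** Section 1.1 plans to recruit 120 participants "within a 15-18 month timeframe". The synopsis and Section 5.1 say that "one-half of participants will be randomized to also receive ACT plus MBRP". Section 4.3 then reasons: "As noted, we have planned for recruitment of eight individuals per month, which corresponds to our target group size". From this it expects at least one new group a month, waits under a month for most, and three groups running at once by the third month. Section 5.1 adds: "We anticipate enrolling approximately eight patients per group". Section 5.2 is looser: "The target number of participants for each group will be up to eight individuals", and "it is possible to conduct the group with as few as four participants or as many as ten". Section 4.3 covers faster recruitment (groups of up to ten) and a backlog above six (a fourth group). It does not cover fewer than four waiting.

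**Timing.**
- Synopsis and Section 3: visits at three and nine months from study entry, equated with end of treatment and six months after it.
- Section 6.1: baseline and randomisation on Day 0, treatment visits from W2, final treatment visit at W13, follow-up at W37, telephone screening from Day -30 to Day -1.
- Section 4.3, on baseline: "This assessment will occur within 14 days (and ideally within 7 days) of screening". On allocation: "Immediately following completion of informed consent and assessment, participants will be randomized to treatment condition". A wait of up to about a month for most then follows.
- Section 6.2.1: for most, screening is under 30 days before entry into the treatment study, explained by the monthly course starts.
- Section 6.2.5: final evaluation for all participants six months after the last treatment session.
- Section 6.2.5.1: payments at weeks 13 and 37.

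**The concern.** Section 4.3 matches a whole-trial recruitment rate to the size of a group that only one arm attends. If the active arm fills at half that rate, groups of about eight, monthly starts and waits mostly under a month cannot all be expected together. Delivery planning matters in a feasibility trial.

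The timing question is distinct. A wait after randomisation falls on the active arm alone. Whether visits are timed from entry or from the last session then decides what the active arm has received when it is assessed, and whether the two arms are followed for the same time. Weekly slopes and six-month outcomes both enter the mediation models in Section 9.1, so an offset in one arm would carry into those comparisons.

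**Working it through.** **1. The plan's own rate.** 120 / 15 = 8.0 a month, which reproduces Section 4.3; at 18 months, 120 / 18 = 6.7. The Section 6.2.5.1 budget agrees: 64 + 56 = 120 baselines. If eight a month meant the active arm alone, the trial would recruit 16 a month and finish in 120 / 16 = 7.5 months, against Section 1.1.

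**2. Inflow to ACT+MBRP.** 8.0 × 1/2 = 4.0 a month; 6.7 × 1/2 = 3.3. Fifteen monthly groups of eight would need 120 people, but the arm has 60 (Section 9.2). Filling one group of eight takes 8 / 4.0 = 2.0 months, or 8 / 3.3 = 2.4.

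**3. Group size with monthly starts.** Simulated with the Section 9.2 blocks (2, 4 and 6 in random order), 120 recruits, and arrivals either even or random (an assumption):

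| Pace | Group below four | Group of eight or more |
|---|---|---|
| 15 months | 16% (even) to 39% (random) of months | 0 to under 2% |
| 18 months | about 56–60% | under 1% |

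**4. What yields.** If starts are held to the next monthly date with four waiting, the mean wait is about 0.6–0.8 month. About 11–17% wait over a month at the 15-month pace and 25–32% at the 18-month pace. The longest waits are about two months or more. If groups are held for eight (even arrivals), 47% wait over a month at 4.0 a month and 70% at 3.3.

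**5. Sections 4.3 and 6.2.1.** Section 4.3 allows up to 14 days plus about a month, roughly 44 days from screening to first session; Section 6.2.1 says under 30. If entry in 6.2.1 means enrolment, 30 days differs from the 14 in 4.3. If it means treatment start, 30 differs from 44.

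**6. Entry clock.** Take a month as 4.348 weeks, the wait from entry to first session as uniform over one month (an assumption), and the last session at wait + 11 weeks.
- Visit at W13 read as day 84 (12 weeks): late if the wait exceeds 1 week; (4.348 − 1) / 4.348 = 77%.
- Visit at three months (13.04 weeks): late if the wait exceeds 2.04 weeks; (4.348 − 2.04) / 4.348 = 53%.
- After a full month's wait, sessions done are floor(12 − 4.348) + 1 = 8, or floor(13.04 − 4.348) + 1 = 9. Those outstanding are sessions 9–12 or 10–12, all MBRP.

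**7. Last-session clock.** Active follow-up falls at wait + 11 + 26.1 weeks after entry: 37.1 with no wait, 39.3 at the mean wait of 2.2 weeks, 41.4 after a month. Standard care at nine months is at week 39.1: almost no mean difference, but about two weeks either way for individuals. Standard care at W37 is at 36 or 37 weeks, a mean difference of about 2–3 weeks.

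**8. W37 against the stated months.** W13 to W37 is 24 weeks, or 24 / 4.348 = 5.5 months, not six. Week 37 is 37 / 4.348 = 8.5 months, not nine.

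**The case against.** Several stronger readings are tempting and do not hold.

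- *Monthly groups cannot run.* Section 5.2 makes eight an upper target and permits four, so groups of about four are allowed, and starting at four keeps most waits under a month. What remains wrong is the equation in Section 4.3, together with the figure of about eight in Section 5.1.
- *Standard care has no follow-up date.* It has two: nine months (synopsis, Section 3) and W37 (Sections 6.1, 6.2.5.1). The defect is that these differ from each other and from the last-session anchor in Section 6.2.5, which standard care cannot use.
- *Most active patients will be assessed before finishing.* Section 6.1 labels W13 the final treatment visit, which supports assessing the active arm at its last session. The 53–77% requires a strict entry clock and an assumed wait distribution.
- *Section 6.2.1 definitely puts the wait before enrolment.* Its next sentence speaks of delayed entry into treatment, so entry may mean treatment start. On neither meaning does it match Section 4.3.

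It is also fair to say that Sections 3, 6.1 and 6.2.5 roughly agree if the wait is near zero, apart from W37. But Section 4.3 does not plan for a near-zero wait. No effect on any estimate has been shown.

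**Conclusion.** The inflow statement in Section 4.3 is wrong as written: the treatment groups receive half the stated rate, which puts expected monthly groups at or just under the permitted minimum. This follows from the plan's own figures. The share of months below four also depends on the assumed arrival pattern.

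The timing conflict is real once the Section 4.3 wait is applied. Its size depends on which clock governs: early end-of-treatment visits on an entry clock, or active follow-up that moves with each patient's wait on a last-session clock. The consequence is confined to the secondary mechanism and clinical-outcome comparisons. The descriptive recruitment and retention results do not depend on it. The point should be corrected, but it does not threaten the trial's primary aim.

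**What to change.** 1. In Section 4.3, restate expected ACT+MBRP inflow as about 4 a month (3.3 at 18 months) and expected group size with monthly starts as about four. Align Section 5.1 and the synopsis. Say whether the start date or the group size yields when fewer than four are waiting.
2. Reconcile the synopsis and Sections 3, 4.3, 6.1, 6.2.1, 6.2.5 and 6.2.5.1 on one time origin used alike in both arms. One option is the next scheduled group start, assigned to each participant before the arm is revealed; if a group slips, the date moves for both arms of that cohort.
3. Make W37 agree with the stated six and nine months, and record actual days from entry and, in the active arm, from the last session.

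**Cost.** Protocol and consent wording plus date fields. With the group-start origin, visits fall about half a month later after entry on average if monthly starts never slip. If starts are held until four are waiting, the shift averages about 0.6–0.8 month, with maxima of about two months or more, and standard care shares it. Baseline is that much older when weekly measures begin, and follow-up ends later. As an illustration only, the budget implies recruitment in months 5–19 (64 / 8 = 8 months in Year 1, 56 / 8 = 7 in Year 2). Follow-up would then end near month 19 + 9 = 28 before any shift, against the planned first quarter of Year 3 (month 27). The month-5 start is inferred, so neither that date nor any movement of payments between years is firm. Maximum participant payments stay at 120 × $270 = $32,400.
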